9.4.2 *Derived Variables for the Primary Objective*

The incidence rate for each event of interest (stroke, major bleeding and death) in AF incidents patients between 2016 and 2019 will be derived by treatment exposure sequence and by unexposed sequence, for overall and by sub-populations (see section 9.2.3.4).

First the treatment exposure sequences will be derived (Table VII). A patient could have several lines i.e., one line by patient by treatment sequence.

Table VII. Derived variables for identification of treatment exposure or unexposed sequences

Variable	Definition
Start date of treatment sequence	
Date variable
 
Equals to the date of the first delivery of each specific treatment (VKA, Apixaban, Rivaroxaban or Dabigatran) of the sequence
 
ATC codes: B01AA, B01AF02, B01AF01, B01AE07 (respectively)

End date of treatment sequence	
Date variable
 
The end date of treatment sequence is defined as:
 
 – The day before the date of first delivery of another OAC if the patient switches to another OAC 
OR

	
 – Date of the last delivery of treatment sequence supplemented by 30 days (treatment duration), at the condition that there is no other OAC reimbursement in the next 60 days 
ATC codes: B01AA, B01AF02, B01AF01, B01AE07
 
For sensitivity analyses: duration of 30 days and 90 days of maximal number of days allowed for being refilled will be considered.

Treatment sequence	
Category variable (VKA / Apixaban / Rivaroxaban / Dabigatran)
 
Equals to “VKA / Apixaban / Rivaroxaban / Dabigatran” if the patient has a reimbursement of VKA, Apixaban, Rivaroxaban or Dabigatran during the treatment sequence
 
ATC codes: B01AA, B01AF02, B01AF01, B01AE07(respectively)

Start date of unexposed sequence	
Date variable
 
The start date of unexposed sequence is defined as:
 
 – The index date for AF patients without an OAC reimbursement in 30 days after the index date (for sensitivity analyses, the inclusion date will be the index date for all incident patients, whether or not patients received OAC therapy within 30 days of the inclusion date) 
OR
 
 – The day after the End date of treatment sequence if the patient has stopped an OAC (at the condition that there is no other OAC reimbursement in the next 60 days, period defined as “the grace period”)

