End date of unexposed sequence	
Date variable
 
The end date of unexposed sequence is defined as:
 
 – The day before the Start date of treatment sequence if the patient starts an OAC 
OR
 
 – End of follow-up period in other cases

Second, each event of interest with the occurred dates available in the data extraction for the AF patients in France during their follow-up will be derived by treatment exposure sequence as indicated in [Table VIII](#).

Table VIII. Derived variables for identifying events of interest

Variable	Definition
Stroke (ischemic or hemorrhagic)	
Binary variable (Yes / No)
 
Equals to “Yes” if the patient is hospitalized with any discharge diagnosis (i.e., main, related or associated diagnosis) of stroke (ischemic or haemorrhagic)

	
ICD-10 codes: I60.x, I61.x, I62.9, I63.x, I64.x, G45.x, G46.x, G81.x, S06.4, S06.5, S06.6
 
Equals to “No” in other cases

Major bleeding	
Binary variable (Yes / No)
 
Equals to “Yes” if the patient is hospitalized with any discharge diagnosis (i.e., main, related or associated diagnosis) of major bleeding
 
ICD-10 codes: I60.x, I61.x, I62.9, S06.4, S06.5, S06.6, I85.0, K22.6, K25.0, K25.2, K25.4, K25.6, K26.0, K26.2, K26.4, K26.6, K27.0, K27.2, K27.4, K27.6, K28.0, K28.2, K28.4, K28.6, K29.0, K62.5, K92.0, K92.1, K92.2, D62, H35.6, H43.1 H45.0, H92.2, I31.2, J94.2, R04.x, K66.1, M25.0, N02, N93.8, N93.9, N95.0, R31, R58, T79.2
 
Equals to “No” in other cases

Death	
Binary variable (Yes / No)
 
Equals to “Yes” if the date of death is reported in DCIR
 
Equals to “No” in other cases

Date of occurrence	
Date variable
 
Equals to the value of date when occurred the event

In the case of a patient presents an event of interest during the grace period, which ends after the end of the study, the event will be considered neither in an exposed nor in an unexposed period, and the patient will be censured at the end of the study period.

Then, the variable presented in [Table IX](#)[Table X](#) will be derived for the analyses of incidence, for each patient, for each event of interest and for each exposure treatment sequence.

Table IX. Derived variables for the analyses of incidence rate on events of interest

Variable	Definition

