Number of occurrences	
Continuous variable
 
Equals to the number of occurrences where the two criteria are met:
 
 – The variable of the specified event of interest (Stroke, Major bleeding or Death) equals “Yes” – The value of the variable Date of occurrence falls in the specific OAC treatment sequence period for exposed patient and during unexposed sequence period for unexposed patient 
In

And finally, the following variables in [Table X](#) will be derived for all patients selected in the study population.

Table X. Derived variables for study population

Variable	Definition
Incident AF patient	
Binary variable (Yes / No)
 
Equals to “Yes” if:
 
 – The patient is newly diagnosed AF during the inclusion period (i.e. no AF diagnostic during the historical period) 
AND
 
 – No reported events of interest (stroke, major bleeding, and death) between the inclusion date and the first date of OAC delivery among AF patients with at least one dispensation of OAC identified within 30 days from inclusion date (cf. 9.2.3.1. Inclusion Criteria) 
Equals to “No” in other cases
 
Sensitivity analyses on incidence rate of stroke, major bleeding and death, and comparison of these events in regression analyzes will be performed on all newly diagnosed AF during the inclusion period (i.e. no exclusion of patients with reported events of interest between inclusion date and index date among those with at least one dispensation of OAC identified within 30 days from inclusion date).

Gender	
Binary variable (Female / Male)
 
See Table IIIError! Reference source not found.

Age	
Categorical variable (<65 years old / 65-74 / 75-79 / ≥80 years old)
 
See Table III

Death	
Binary variable (Yes / No)
 
See Table III

Lost to follow-up	
Binary variable (Yes / No)
 
Equal to “Yes” if the patient has no consumption or reimbursement of care in the 12 months following the date of last consumption
 
Equals to “No” in other cases

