9.4.3.2 Comparison of the incidence of stroke, major bleeding, death

The incidence rate ratio for each event of interest (stroke, major bleeding and death; see [Table VIII](#) for derivation of events of interest) will be compared using a Cox regression model with OAC exposure (see [Table VII](#) for derivation of exposure sequences) considered as time-dependent variable adjusted for covariates. Covariates will be derived at index date as indicated in [Table XV](#).

Table XV. Derived variables for confounders

Variable	Definition
Age	Categorical variable (<80 years old / 80–90 / >90 years old) See Table III
Sex	Binary variable (Female / Male) See Table III
Prescriber's specialty at initiation of OAC	Categorical variable (Hospital-based physician/ City cardiologist/ Generalist practitioners/Other) See Table III
Having Malnutrition	Binary variable (Yes / No) See Table III
Risk of falls	Binary variable (Yes / No) See Table III
Frail patients	Binary variable (Yes / No) See Table V
Morbid obesity	Binary variable (Yes / No) See Table VI
At least one visit to a nursing home	Binary variable (Yes / No) See Table VI
Concomitant treatments	Binary variable (Yes / No) for each concomitant treatment listed in Table XIV

For example, for antiplatelet drugs, equals to “Yes” if the patient has at least one reimbursement for an antiplatelet drug in the 4 months before the index date
	
HAS-BLED score	Categorical variable (0, 1, 2, 3, ≥ 4) See Table VI
CHAD₂DS₂VASC score	Categorical variable (0, 1, 2, 3, 4, ≥ 5) See Table VI
Age adjusted Charlson Cormordity Index (ACCI) adapted to SNDS data	Categorical variable (0, 1-2, 3-4, ≥ 5) See Table VI XII

9.4.3.3 *Estimation of the AF annual standardized incidence rate and prevalence*

All the variables in [Table XVI](#) will be derived for all AF patients in France in 2016, 2017, 2018 and 2019.

Table XVI. Derived variables for incidence and prevalence

Variable	Definition
Incident AF patient	Binary variable (Yes / No) See Table X
Prevalent AF patient	Binary variable (Yes / No) Equals to “Yes” if the patient is diagnosed AF during the historical period Patients belonging to the study population

9.4.3.4 *To describe the use of oral anticoagulants (OACs) in AF patients initiating treatment (AF patients exposed to OAC therapy)*

Table XVII. Derived variables for OAC treatment pattern

Variable	Definition

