- $N_{i,Y}$ represents the counts of patients at risk (French adult residents from census data in year Y minus count of prevalent diagnosed AF patients in year Y) in the age group i in the year Y

The estimations of the annual standardized incidence and annual prevalence of AF will be also performed according to exposure status (exposed to OAC or unexposed), every year. A patient will be considered exposed to OAC in a given year if the patient presents at least one sequence treatment for an OAC in the corresponding year.

9.7.4.4 Description of the use of oral anticoagulants (OACs) in AF incident patients initiating treatment (AF patients exposed to OAC therapy)

The analysis of the OAC treatment patterns will be descriptive and exploratory in nature.

The date of first reimbursement of any drugs of interest (VKA, apixaban, rivaroxaban, and dabigatran) will be considered as the regimen initiation date and mark the beginning of the identification of the treatment sequence (cf. table VII).

The duration of a prescription will be of 30 days for any drugs of interest. The grace period considered for any drugs of interest considered will be 60 days (30 days and 90 days will be considered for sensitivity analyses).

A treatment sequence will continue until one of the following occurs:

- A regimen switch, defined as the reimbursement of another OAC. The end date of the first treatment sequence is the day before the date of first reimbursement of another OAC.
- Discontinuation of drugs in the treatment sequence: if a period between two consecutive claims is superior to the duration of the treatment of the last claim, plus a permissible gap of at least 60 days (30 and 90 days for sensitivity analyses) then the medication is considered as stopped within the treatment sequence. The date of discontinuation (end date of the treatment sequence) will be fixed at the date of the last claim, plus the treatment duration of this last claim.
- End of follow-up.

The treatment pattern analysis will be providing the following information:

- Number and percentage of patients receiving each of OAC treatment during the follow-up
- Number and percentage of patients who received 1, 2, 3, 4 and 5+ sequence treatment during the follow-up
- Number and percentage of patients who have switched from an OAC to another during the follow-up

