9.7.6 Sensitivity analyses

We will perform the following sensitivity analyses:

1. Analyses on the evaluation of the incidence rate and comparison of the events of interest (stroke, major bleeding, and death) will be performed from the inclusion date for all incident AF patients (i.e. the inclusion date will be the index date for all incident patients, whether or not patients received OAC therapy within 30 days of the inclusion date).
2. Analyses including the 2020 data (given the uncertainty of the impact of the Covid 19 health crisis on the management of NVAF incident patients) will be conducted on:
 - Description of the follow-up of the study population (Table A1);
 - Sociodemographic characteristics (Tables A4 and A7), medical history and comorbidities (Table A5 and A8); concomitant treatments (Tables A6 and A9);
 - Estimation and comparisons of the incidence of interest-events in AF exposed and unexposed to OAC (primary objective - Table A2, secondary objective - Table A10);
 - Estimation of the annual incidence rate and the prevalence of AF patients (Tables A12 and A13 respectively).
3. Analyses on AF patients without the second inclusion criteria (new OAC users identified by the algorithm of *Billionnet et al.* not included) will be performed for the estimation of the annual standardized incidence and prevalence (Tables A12 and A13 respectively).
4. Analyses will be considered to test the impact of different grace periods (duration of 30 days and 90 days) in the calculation of treatment sequences for the following objectives:
 - Estimation and comparisons of the incidence of interest-events in AF exposed and unexposed to OAC (primary objective - Table A2, secondary objectives - Table A10)
5. If more than 10% of each event of interest occur during the 60 days grace period, analyses will be performed considering this event of interest in an unexposed period for the following objectives:

- Estimation and comparisons of the incidence of interest-events in AF exposed and unexposed to OAC (primary objective - Table A2, secondary objectives - Table A10)

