Death	xx.x (xx.x)	xx.x (xx.x)	xx.x (xx.x)
Lost to follow-up	xx.x (xx.x)	xx.x (xx.x)	xx.x (xx.x)
End of study period	xx.x (xx.x)	xx.x (xx.x)	xx.x (xx.x)
Duration of the follow-up in years			
Mean (std)	xx.x (xx.x)	xx.x (xx.x)	xx.x (xx.x)
Median	xx.x	xx.x	xx.x
Q1 - Q3	xx.x - xx.x	xx.x - xx.x	xx.x - xx.x
Min - Max	xx.x - xx.x	xx.x - xx.x	xx.x - xx.x
Duration group of the follow-up in years: n (%)			
[0-1[xx.x (xx.x)	xx.x (xx.x)	xx.x (xx.x)
[1-2[xx.x (xx.x)	xx.x (xx.x)	xx.x (xx.x)
[2-3[xx.x (xx.x)	xx.x (xx.x)	xx.x (xx.x)
[3-4[xx.x (xx.x)	xx.x (xx.x)	xx.x (xx.x)
[4-5]*	xx.x (xx.x)	xx.x (xx.x)	xx.x (xx.x)

*This category will be display only for the sensitivity analysis (up to 2020)

2. Shell Tables and Figures of Results of the Planned Analysis for the Primary Objective

Table A2. Incidence rate for stroke, major bleeding and death in AF incidents patients between 2016 and 2019 in France – <POPULATION>

<POPULATION>	Stroke				Major bleeding				Death			
	n	N	Crude	Standardized **	n	N	Crude	Standardized %**	n	N	Crude	Standardized **
Overall	x	x	x,x [x,x;x,x]	NA	x	x	x,x [x,x;x,x]	NA	x	x	x,x [x,x;x,x]	NA
CI 95%				NA				NA				NA
Unexposed to OAC*	x	x	x,x [x,x;x,x]	x,x [x,x;x,x]	x	x	x,x [x,x;x,x]	x,x [x,x;x,x]	x	x	x,x [x,x;x,x]	x,x [x,x;x,x]
CI 95%												
Exposed to OAC	x	x	x,x [x,x;x,x]	NA	x	x	x,x [x,x;x,x]	NA	x	x	x,x [x,x;x,x]	NA
CI 95%				NA				NA				NA
VKAs	x	x	x,x [x,x;x,x]	NA	x	x	x,x [x,x;x,x]	NA	x	x	x,x [x,x;x,x]	NA
CI 95%				NA				NA				NA
DOACs	x	x	x,x [x,x;x,x]	NA	x	x	x,x [x,x;x,x]	NA	x	x	x,x [x,x;x,x]	NA
CI 95%				NA				NA				NA
Apixaban	x	x	x,x [x,x;x,x]	NA	x	x	x,x [x,x;x,x]	NA	x	x	x,x [x,x;x,x]	NA
CI 95%				NA				NA				NA
Dabigatran	x	x	x,x [x,x;x,x]	NA	x	x	x,x [x,x;x,x]	NA	x	x	x,x [x,x;x,x]	NA
CI 95%				NA				NA				NA
Rivaroxaban	x	x	x,x [x,x;x,x]	NA	x	x	x,x [x,x;x,x]	NA	x	x	x,x [x,x;x,x]	NA
CI 95%				NA				NA				NA

OAC: Oral anticoagulant; DOACs: Direct oral anticoagulants; VKAs: Antivitamins K; NA, not applicable.

n: number of events of interest; N: number of person-years of follow-up

*Unexposed and exposed to OAC correspond to the period of time where the patients are not exposed to OAC and exposed to OAC, respectively

%: Incidence of the event of interest; CI 95%: 95% confidence interval

**: Standardized on age group (<65 years old; 65-74 years old; 75-79 years old; ≥80 years old) using the exposed population as reference

<POPULATION>: Incidence rate of events will be stratified in the following sub-groups:

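### Table VII decides exposure on days 31–90 after a delivery by whether a refill follows, so deaths in that window count as unexposed while late refillers keep the same days as OAC time

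*SAP*

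**What the plan says.** Table VII in SAP Section 9.4.2 ends a sequence without a switch at the last delivery "supplemented by 30 days (treatment duration), at the condition that there is no other OAC reimbursement in the next 60 days". An unexposed sequence after treatment starts on "The day after the End date of treatment sequence if the patient has stopped an OAC". Table IX counts an event as exposed when "The value of the variable Date of occurrence falls in the specific OAC treatment sequence period for exposed patient", and as unexposed when its date lies in an unexposed sequence.

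Both event analyses use these sequences. The Table A2 footnote says that its unexposed and exposed rows "correspond to the period of time where the patients are not exposed to OAC and exposed to OAC, respectively". Section 9.4.3.2 cites Table VII "for derivation of exposure sequences) considered as time-dependent variable adjusted for covariates".

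Three other places bear on the same days:

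- The text after Table VIII (9.4.2) makes an exception when the grace period runs past study end: "the event will be considered neither in an exposed nor in an unexposed period".
- Section 9.7.4.4, on treatment patterns, ends a sequence "if a period between two consecutive claims is superior to the duration of the treatment of the last claim, plus a permissible gap" of 60 days, and also lists end of follow-up as a way a sequence ends.
- Section 9.7.6 item 4 repeats the event analyses with grace periods of 30 and 90 days. Item 5 treats grace-period events as unexposed, but only if they exceed 10%.

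**The concern.** Take two patients with the same last delivery. One refills on day 60. The end condition is not met, so days 31–60 stay OAC time. The other dies on day 60. No reimbursement follows, so the sequence ends on day 30, and days 31–60 and the death become unexposed. The same days are classified differently according to something that happens later and that death prevents. This is immortal time built into the exposure definition, and covariate adjustment cannot remove it.

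Death is one of the three primary outcomes. The rule lowers OAC death rates, raises unexposed death rates, and raises the unexposed-versus-VKA hazard ratio for death. Strokes and bleeds are affected only when the patient does not refill after the event. DOAC-versus-VKA contrasts are affected only when refill timing differs by drug.

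**Working it through.** **Window.** 30 covered days + 60 days of grace = 90, so the days in question are 31–90. Table VII does not say whether the 60 days run from the delivery or from the end of supply; Section 9.7.4.4 makes it the latter.

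**Inputs.** The plan gives no death rate or refill timing, so these are assumptions: 10 deaths per 100 person-years (PY) on and off OAC (true ratio 1.00), on-time refills on days 25–30 (mean 27.5), late refills uniform from day 31 to day *U*, 2% stopping per refill, 30% never treated, entry uniform over four years.

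**First-order check of the OAC rate.** Let *p* be the late share, *m* the mean late refill day and *T* the mean OAC time per refill cycle.

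- *T* = (1 − *p* − 0.02) × 27.5 + 0.02 × 30 + *p* × *m*
- Table VII keeps the late refillers' gap time, *p*(*m* − 30), but sends the deaths in it to unexposed. The OAC rate is therefore about 10 × [1 − *p*(*m* − 30)/*T*].

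| *p* | *U* | *m* | *T* | OAC rate per 100 PY |
|---|---|---|---|---|
| 10% | 45 | 38 | 24.2 + 0.6 + 3.8 = 28.6 | 10 × (1 − 0.8/28.6) = 9.7 |
| 10% | 90 | 60.5 | 24.2 + 0.6 + 6.05 = 30.85 | 10 × (1 − 3.05/30.85) = 9.0 |
| 25% | 45 | 38 | 20.075 + 0.6 + 9.5 = 30.175 | 10 × (1 − 2.0/30.175) = 9.3 |
| 25% | 90 | 60.5 | 20.075 + 0.6 + 15.125 = 35.8 | 10 × (1 − 7.625/35.8) = 7.9 |

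**Simulation** (300,000–600,000 patients per scenario for rates, 400,000 for Cox; end-of-study exception applied). Rates are per 100 PY.

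| Late refills | OAC | Unexposed | Ratio | Cox HR for death, unexposed vs VKA (95% CI) |
|---|---|---|---|---|
| None | 10.0 | 10.0 | 1.00 | 0.99 |
| 10%, by day 45 | 9.7 | 10.3 | 0.94 | 1.05 (1.03–1.07) |
| 10%, to day 90 | 9.1 | 11.0 | 0.83 | 1.21 (1.19–1.23) |
| 25%, by day 45 | 9.3 | 10.7 | 0.87 | 1.15 (1.13–1.17) |
| 25%, to day 90 | 8.0 | 12.3 | 0.65 | 1.55 (1.52–1.58) |

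Varying never-treated to 20–40%, stopping to 1–4% and deaths to 5–15 per 100 PY moves the ratio to 0.80–0.86 (10%, day 90) and 0.62–0.70 (25%, day 90). If late refills all come by day 38, it is 0.96–0.99 (10%) and 0.92–0.95 (25%). A separately coded run with 30% late to day 90 gave 7.88 and 12.60, a ratio of 7.88/12.60 = 0.63.

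**Do the planned analyses help?**

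- Item 4, grace of 30 / 90 days: 0.93 / 0.94 at 10% late by day 45, and 0.89 / 0.65 at 25% late to day 90. The look-ahead stays.
- Item 5: grace-period deaths are 3–18% of deaths in OAC starters. At 10% late to day 90 they are 9.9%, so the trigger does not fire although the ratio is 0.83. If it fires, it moves deaths to where Table VII already puts most of them.
- The end-of-study exception is small: in the separate run it removed 478 of 10,672 deaths on days 31–90 (4.5%).

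**Other contrasts.** DOAC versus VKA for death reads 1.00 at equal late shares, 0.97 to 0.89 if 25% of DOAC and 10% of VKA refills are late, and 1.04 to 1.13 in reverse. For non-fatal events, OAC:unexposed reads 1.00–1.01 if everyone refills afterwards, 0.97–0.99 if 10% do not, and 0.81–0.97 if half do not.

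**Past-only rules.** With exposure carried to day 90, or stopped at day 30, for every patient whether or not a refill follows, the death rate ratio is 0.98–1.02. The Cox HR under the 30+60 rule is 0.99–1.00.

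**The case against.** The strongest objection is that the SAP can be read in other ways, and the sign depends on the reading. Section 9.7.4.4 cites Table VII, requires two consecutive claims before a stop is declared, and lists end of follow-up as a sequence end. On that reading a death in the gap stays on OAC, and the OAC:unexposed ratio becomes 1.06–1.10. Item 5 also makes most sense if the main analysis does not already count grace-period events as unexposed. If those deaths belonged to neither group, the ratio would be 1.04 with no late refills, 1.01 to 0.95 at 10% late and 0.97 to 0.83 at 25%.

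These readings do not displace Table VII. Section 9.7.4.4 serves the descriptive treatment-pattern objective, whereas Sections 9.4.2 and 9.4.3.2 name Table VII for the event analyses, and Table VII has no end-of-follow-up branch. Item 5 keeps a function under the literal rule: it would move gap strokes and bleeds followed by a refill, which Table VII counts as exposed. What stands is that the SAP does not give one clear rule for grace-period events, which is a further reason to write one.

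It is also fair that the firm effect is confined to death, on versus off OAC, that the largest figures need 25% of refills late and spread to day 90, and that no delivery-based rule fully handles patients who stop OAC because they are dying.

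**Conclusion.** The concern holds. As written, Table VII uses future refills to assign days 31–90 and biases OAC death rates down, unexposed death rates up, and the unexposed-versus-VKA hazard ratio for death up. The direction follows from the rule whenever some refills are late; with none late there is no bias. The size rests on assumed refill timing and runs from a few per cent to roughly a one-third false reduction in the OAC:unexposed death rate ratio. This should be corrected before data access.

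**What to change.** In Section 9.4.2, add one exposure variable for the event-rate and Cox analyses that uses past deliveries only. Using the SAP's own figures: exposed to the last delivered OAC until delivery + 30 + 60 days, or an earlier switch, death or end of follow-up, whether or not a refill follows; unexposed from the next day until the next delivery; each event takes the status on its date. The alternative is a 30-day window, with unexposed time from day 31 until the next delivery. Name one as primary, and run the other unconditionally in place of item 5 of Section 9.7.6. Apply item 4 to the new rule. Delete the end-of-study exception after Table VIII. Keep last claim + 30 days for duration and persistence, and state in 9.7.4.4 that its sequence ends do not assign events.

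The cost is a few lines of SAP text and one variable; duration and persistence results do not change. The 30+60 rule counts up to 60 days after a true stop as exposed. In simulation a true ratio of 0.70 reads 0.71–0.77 with 30+60, 0.69–0.74 with 30 days and 0.45–0.70 with Table VII. If 10–25% of deaths follow 45–60 days without deliveries because of terminal illness, with no drug effect, the readings are 0.96–1.00, 0.61–0.84 and 0.52–0.83. If that phase lasts 90 days, all three read 0.53–0.64. Neither window is best in every case, so both should be reported.

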Appendix 3 Identification of events of interests: stroke and major bleeding

Title	ICD-10 code
Unspecified, ischemic stroke (including Transient ischemic cerebral (TIC))	I63, I64, G46, G81, G45
Hemorrhagic stroke (including intracranial bleeding)	I60, I61, I62.9, S064, S065, S066
Gastric, duodenal and rectal bleeding	I850, K226, K250, K252, K254, K256, K260, K262, K264, K266, K270, K272, K274, K276, K280, K282, K284, K286, K290, K625, K920, K921, K922
Acute posthemorrhagic anemia	D62
Intraocular bleeding	H356, H431 H450
Otorragia	H922
Hemopericardium	I312
Respiratory bleeding	J942, R04
Haemoperitoneum	K661
Intra articular bleeding	M250
Uterine and vaginal bleeding	N02, N938, N939, N950, R31
Other bleeding	R58, T792

Stroke

Major bleeding

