Ulcer disease	Binary variable (Yes / No)
	Derived based on (20,23)
	Equals to “Yes” if the patient meets any criterion below on or in the 2 years prior to the index date:
	
 - Is hospitalized at least once with any diagnosis (i.e., main, related or associated diagnosis) of ulcer disease
	ICD-10 codes: K25.x, K26.x, K27.x, K28.x
	OR
	
 - Is covered by the LTD status for ulcer disease at least one day
	ICD-10 codes: K25.x, K26.x, K27.x, K28.x
	Equals to “No” in other cases
Hemiplegia (for ACCI derivation)	Binary variable (Yes / No)
	Derived based on (20,23)
	Equals to “Yes” if the patient meets any criterion below on or in the 2 years prior to the index date:
	
 - Is hospitalized at least once with any diagnosis (i.e., main, related or associated diagnosis) of hemiplegia
	ICD-10 codes: G04.1, G11.4, G80.1, G80.2, G81.x, G82.x, G83.0, G83.1, G83.2, G83.3, G83.4, G83.9
	OR
	
 - Is covered by the LTD status for hemiplegia at least one day

ICD-10 codes: G04.1, G11.4, G80.1, G80.2, G81.x, G82.x, G83.0, G83.1, G83.2, G83.3, G83.4, G83.9
 
Equals to "No" in other cases
	

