Bleeding history or predisposition (for HAS-BLED score derivation)	
Binary variable (Yes / No)
 
Equals to “Yes” if the patient is hospitalized with hospital-discharge summary with primary diagnosis of bleeding on or in the 2 years prior to the index date:
 
ICD-10 codes: D62, D683, D698, D699, H113, H313, H356, H431, H450, H922, I230, I312, I600-I616, I618-I621, I629, I850, I983, J942, K250, K252, K254, K256, K262, K264, K270, K272, K274, K276, K280, K282, K284, K286, K661, K920, K921, K922, M250, N020-N029, N421, N920, N921, N923, N924, N938, N939, N950, R040, R041, R042, R048, R049, R31, R58, S064, S065, S066, S260, S271, T792
 
Equals to “No” in other cases

Labile international normalized ratio (INR) (for HAS-BLED score derivation)	
Binary variable (Yes / No)
 
Not applicable to SNDS data (INR results are not captured in SNDS databases).

Elderly (for HAS-BLED score derivation)	
Binary variable (≤ 65 years old / > 65 years old)

Drugs predisposing to bleeding or alcohol concomitantly (for HAS-BLED score derivation)	
Binary variable (Yes / No)
 
Variable Drugs equals to “Yes” if the patient has at least one drug dispensation for antiplatelet agents (acetylsalicylic acid: B01AC06 ATC code, clopidogrel: B01AC04 ATC code) or NSAIDs (M01A ATC code) in the 4 months before the index date.
 
OR

	
Variable Alcohol equals to “Yes” if the patient is hospitalized with any discharge diagnosis (i.e., main, related or associated diagnosis) of all causes related to alcohol on or in the 2 years prior to the index date:
 
ICD-10 codes : E244, E512, F10, G312, G621, G721, I426, K292, K70, K860, R780, T51, X45, X65, Y15, Y90, Y91, Y573, Z502, Z714, Z721.
 
Equals to “No” in other cases

HAS-BLED score	
Continuous variable (between 1 and 9)
 
Derived based on (19)
 
Equals to sum of:
 
 ○ 1 point if the variable Hypertension equals to “Yes” ○ 1 or 2 points if the variable Abnormal renal and liver function equals to “Yes” (1 point each) ○ 1 point if the variable Stroke equals to “Yes” ○ 1 point if the variable Bleeding equals to “Yes” ○ 1 point if the variable Labile INRs equals to “Yes” ○ 1 point if the variable Elderly equals to “>65 years old” ○ 1 or 2 points if the variable Drugs or alcohol equals to “Yes” (1 point each)

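### Hemiplegia (G81) coded in any diagnosis position counts as a new stroke, and I62.0/I62.1 haemorrhage is in neither the stroke nor the major-bleeding outcome

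*SAP*

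**What the plan says.** **Stroke outcome.** SAP Section 9.4.2, Table VIII, sets stroke to Yes when the patient is "hospitalized with any discharge diagnosis (i.e., main, related or associated diagnosis) of stroke (ischemic or haemorrhagic"), with the codes "I60.x, I61.x, I62.9, I63.x, I64.x, G45.x, G46.x, G81.x, S06.4, S06.5, S06.6". Protocol Appendix 3 has the same content. It puts G81 in the ischemic row and gives "I60, I61, I62.9, S064, S065, S066" for the hemorrhagic row, whose label says that intracranial bleeding is included.

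**Major-bleeding outcome.** The Table VIII list opens "I60.x, I61.x, I62.9, S06.4, S06.5, S06.6, I85.0, K22.6". Its only I62 code is also I62.9.

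**Other uses of G81 in the SAP.**
- Table VI, hemiplegia item of ACCI: "Is hospitalized at least once with any diagnosis (i.e., main, related or associated diagnosis) of hemiplegia", with codes beginning "G04.1, G11.4, G80.1, G80.2, G81.x, G82.x, G83.0". The item scores 2 points.
- Table V, previous stroke: G81.x qualifies alone, through a hospital stay or long-term-disease (LTD) status.
- Table VI, stroke history by type: G81 is classed as ischemic.
- Section 9.4.3.1, HAS-BLED previous-stroke item: G81 is listed.

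**Other uses of I62.0 and I62.1.** The HAS-BLED bleeding history (Section 9.4.3.1) includes "I600-I616, I618-I621, I629". The ACCI cerebrovascular item (Table VI) takes all of I62.x.

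**Counting.** SAP 9.7.3.1 counts the first occurrence of each event and standardises the unexposed rates by age. Previous stroke is a named subgroup of the primary objective (SAP 8.1).

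**The concern.** Stroke and major bleeding are two of the three primary outcomes, and both are defined only by these code lists.

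G81 describes a deficit that can persist after a stroke. The SAP treats it that way when it scores hemiplegia as a baseline comorbidity. After the index date the same code, in the same positions, becomes a new event. An old stroke can therefore generate a new one whenever the residual deficit is recorded at an unrelated admission. The patients most open to this are those in the previous-stroke subgroup.

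The I62 gap is the reverse problem. The SAP regards I62.0 and I62.1 as bleeding when it looks back, but not when it looks forward. In a study of anticoagulant exposure, that leaves a type of intracranial bleed outside the primary safety outcome.

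**Working it through.** The plan gives no figure that depends on these codes, so there is nothing to reproduce. The check is list membership.

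| Code | Stroke outcome | Major-bleeding outcome | ACCI | HAS-BLED bleeding history |
|---|---|---|---|---|
| G81 | in | out | hemiplegia, 2 points | out (but in its previous-stroke item) |
| I62.0, I62.1 | out | out | cerebrovascular disease, 1 point | in (range I618 to I621) |
| I62.9 | in | in | cerebrovascular disease, 1 point | in |
| S06.4 to S06.6 | in | in | out | in |

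The names of the I62 and S06 subcodes come from ICD-10; the documents do not label them one by one. The inconsistency for I62.0 and I62.1 does not depend on the names.

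**G81, followed through the rules.**
1. A patient has G81 recorded in the two years before index. Table V puts the patient in the previous-stroke subgroup, even with no acute stroke code.
2. Pre-index events lead to exclusion only within 30 days before index, and only where the inclusion date is not the date of the first anticoagulant dispensation (SAP 9.2.3.3.2). Older hemiplegia passes.
3. During follow-up the patient is admitted for another reason, with G81 as an associated diagnosis. Table VIII records a stroke on that stay. No rule asks for a main diagnosis, an acute code in the stay, or a lookback free of G81.
4. Only the first occurrence counts, so a later true stroke in this patient cannot enter the primary rate.
5. The event falls in the ischemic column of Table A3. Its date also sets the 6- and 12-month windows around the first stroke for objective 7 when it follows anticoagulant initiation.

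**I62.0 and I62.1.** A stay with one of these codes and no other listed code is neither a stroke nor a major bleed. The same code before index, as primary diagnosis, would score a HAS-BLED bleeding point.

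**Would a planned analysis show this?** SAP 9.7.6 varies the index date, the 2020 data, the algorithm-identified patients, the grace period, and the handling of events in the grace period. None varies outcome codes or diagnosis position.

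**Illustration only.** Let f be the share of reference-group strokes that are false, and suppose that false strokes arise at the same rate in both groups. Then observed ratio = (1 − f) × true ratio + f. For a true ratio of 0.70:
- f = 5%: 0.95 × 0.70 + 0.05 = 0.715
- f = 10%: 0.90 × 0.70 + 0.10 = 0.73
- f = 20%: 0.80 × 0.70 + 0.20 = 0.76
- f = 30%: 0.70 × 0.70 + 0.30 = 0.79

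Both f and the equal-rate condition are assumptions. If residual hemiplegia is unevenly spread over the exposure groups, the direction can differ.

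**The case against.** The best defence has four parts.

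**G81 is a deliberate stroke code.** It appears in Protocol Appendix 3, previous stroke, stroke history by type and the HAS-BLED stroke item, and some G81 stays are acute strokes. This stands as far as it goes: not every G81 stay is a false event. But the code does not distinguish acute from old, and consistent use of it as stroke does not remove the conflict with its use as a comorbidity.

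**The models adjust.** The Cox models include history of stroke, risk of falls and nursing-home visits (SAP 9.7.4.2), and Table XV adds frailty and ACCI, which itself scores hemiplegia. This weakens the argument about between-group comparison. It does nothing for the primary rates, which are crude or standardised by age only, and adjustment for covariates does not turn a false event into a true one.

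**Baseline scores come from separate publications** and need not share an outcome list. That is fair. However, the documents give no reason to count I62.0 and I62.1 as bleeding in history and not in follow-up.

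**S06.4 to S06.6 are a declared choice.** A reader might infer that traumatic head bleeds are in the stroke list by mistake, or that counting them under both outcomes is an error. The documents do not support this. The protocol row says that it includes intracranial bleeding, I60, I61 and I62.9 also sit in both lists, the outcomes are analysed independently, and ischemic and hemorrhagic stroke are reported separately. At most this is a labelling comment.

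**Conclusion.** The point holds in two parts. G81 without an acute code can turn residual hemiplegia into a first stroke, chiefly in the previous-stroke subgroup. I62.0 and I62.1 are missing from both outcomes when they stand without another listed code. Both follow from the text, touch primary outcomes, and would go unseen under the planned sensitivity analyses. They should be settled before the outcomes are derived.

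The size is unknown. The documents give no frequency for any of these codes, no admission rate and no prevalence of residual hemiplegia.

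Three stronger conclusions are tempting and are not supported:
- **A specific rate of false strokes, or a comparison with true recurrence.** Every input would be an assumption, and the first-occurrence rule limits each patient to one event.
- **That every I62.0 or I62.1 bleed is lost.** Any diagnosis position counts, so a stay also coded G81 is captured as stroke and one also coded D62 as major bleeding.
- **That bleeding on anticoagulants is understated relative to no exposure.** Nothing in the documents shows how these codes divide between exposed and unexposed time.

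**What to change.** In SAP Table VIII and Protocol Appendix 3:
- Count G81 as stroke only when the same stay also carries I60, I61, I62, I63 or I64.
- Add I62.0 and I62.1 to major bleeding and to the intracranial/hemorrhagic stroke category.

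Make the same changes in the matching history variables, so that subgroup and baseline definitions agree with the outcome: previous stroke (Table V), stroke history by type and history of major bleeding (Table VI), and G81 in the HAS-BLED previous-stroke item (Section 9.4.3.1). Where LTD status also qualifies there is no hospital stay, so the SAP should state the equivalent rule for G81 there.

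Keep the current list as a named sensitivity analysis in SAP 9.7.6, for comparability with earlier studies.

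Optionally, report S06.4 to S06.6 separately as traumatic intracranial bleeding. G46 can stay as it is.

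The cost is an edit to both documents and one extra run. There will be somewhat fewer stroke events, and direct comparability falls for the main analysis. Because the Table V variable feeds the CHA2DS2-VASc score, membership of the previous-stroke subgroup and of the risk strata will also shift.
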